10.3 Data Analyses Plans**10.3.1 Primary Objective**

To evaluate the safety of NU-0129 SNA gold nanoparticle infusion in patients with recurrent GBM or GS, we will count and record the number of adverse events.

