2.0 OBJECTIVES & ENDPOINTS

2.1 Primary Objective & Endpoint

- The primary objective is to assess the safety of intravenous NU-0129 in patients with recurrent GBM or GS.
- The total incidence of adverse events will be evaluated using CTCAE v4.03 from the time of informed consent to 21 days after study drug administration. Adverse events will be monitored during and immediately after the infusion as well as weekly for 21 days after treatment administration.

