4.0 TREATMENT PLAN

4.1 Overview

The phase 0 trial will evaluate the safety, pharmacokinetics, and bio-distribution of a systemically (IV) administered SNA gold nanoparticle, NU-0129. Once registered, eligible patients will receive intravenous NU-0129 one time as an inpatient followed by tumor resection within 8-48 hours post-infusion. Patients will be monitored with telemetry, vital signs and labs before and after the infusion as indicated in section 5.0. Bio-distribution will be analyzed with PK blood draws over 24 hours and collection of tissue during the scheduled surgery.

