4.6 Duration of Therapy

Within 14 days of study registration, patients will receive intravenous NU-0129 one time at nominal dose 0.04mg/kg. Patients will be admitted the morning of the planned NU-0129 infusion, and a tumor resection will occur 8-48 hours after administration. Patients will remain inpatient for standard of care post-operative procedures, including an MRI of the brain. Discharge will take place when clinically appropriate.

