5.0 STUDY PROCEDURES

Table 5.1 – On-Study Procedures (**see table 5.2 for follow-up procedures)

Time Period	Screening ¹	Inpatient		
		Treatment Administration	Surgery	Post-op ¹²
Informed Consent ¹	X			
Medical history	X			
Physical exam ²	X			X
Karnofsky PS	X			X
Vitals	X	X ³	X	
Toxicity assessment	X	X		X ¹³
Conmeds	X	X		X
MRI ⁴	X			X
CBC with diff ⁵	X	X ⁵		X
Chemistry panel ⁵	X			X
Phosphorus + Mg ⁵	X	X		X
PT/PTT/INR ⁵	X			X
Cholesterol panel ⁵	X			X
Urinalysis	X			
Pregnancy test ⁶	X			
ECG	X			X ⁷
NU-0129 Infusion ⁸		X		
Tumor Resection			X ¹¹	
PK blood samples		X ⁹		
Tissue collection	X ¹⁰			X ¹¹

¹ All screening procedures must be completed within 14 days of registration unless otherwise noted (Labs and pregnancy test must be within 14 days of registration). Informed consent can be within 28 days prior to registration.

² Includes complete neurologic exam and weight. Height will be recorded at screening.

³ Vital signs should include pulse and blood pressure. On the day of treatment administration, vitals will be measured using continuous telemetry immediately prior to, during, and for at least 8 hours post infusion. Vital signs will then be measured at least every 4 hours for a total of 24 hours post-infusion. Vital signs will also be assessed continuously throughout the patient's surgical resection.

⁴ A brain MRI with and without contrast will be performed at baseline (within 21 days of registration) and after surgery as part of standard of care post-op procedures, likely within 48 hours of surgical resection.

⁵ Laboratory tests (including, CBC, Chemistry, PT/PTT/INR, Phosphorus, Mg, and Cholesterol panel) must be drawn within 7 days of registration and treatment. If treatment occurs more than 7 days after the indicated labs, they should be repeated. CBC w/ differential should include WBC, ANC, ALC, and Platelets. A complete chemistry panel will be drawn including Sodium, Potassium, Chloride, Bicarbonate, BUN/Creatinine, AST, ALT, Total Bilirubin, Calcium, and Albumin. CBC with diff will be repeated pre-dose on the day of study treatment.

⁶ A pregnancy test will be performed for females of child-bearing potential at screening (serum or urine) within 14 days of registration.

⁷ An ECG will be performed at screening and only as needed for standard of care toxicity management during post-operative observation.

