6.2 Primary Endpoint

Safety will be measured by recording adverse events using CTCAE v4.03 from the time a patient signs consent to 21 days after study drug administration. Any patient who has received at least a partial dose of NU-0129 will be evaluable for this endpoint. If a patient has a continuing adverse event at 21 days which is related to treatment, it will be followed until resolution to baseline or Grade ≤ 2.

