7.3.2 Determining if Expedited Reporting is Required

This includes all events that occur within 30 days of the last dose of protocol treatment. Any event that occurs more than 30 days after the last dose of treatment and is attributed (possibly, probably, or definitely) to the agent(s) must also be reported accordingly.

- 1) Identify the type of adverse event using the NCI CTCAE v 4.03.
- 2) Grade the adverse event using the NCI CTCAE v 4.03.
- 3) Determine whether the adverse event is related to the protocol therapy.

Attribution categories are as follows:

- Definite: AE is clearly related to the study treatment.
- Probable: AE is likely related to the study treatment.
- Possible: AE may be related to the study treatment.
- Unlikely: AE not likely to be related to the study treatment.
- Unrelated: AE is clearly NOT related to the study treatment.

- 4) Determine the prior experience of the adverse event.

Expected events are those that have been previously identified as resulting from administration of the agent. An adverse event is considered unexpected, for expedited reporting purposes only, when either the type of event or the severity of the event is not listed in:

- the current protocol
- the drug package insert
- the current Investigator's Brochure

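### The primary safety result is one undivided adverse event count that pools pre-dose, pre-incision and post-operative events; it should be split at dosing and at incision

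*Combined protocol and SAP*

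**What the plan says.** The analysis of the primary objective in section 10.3.1 is one sentence: "we will count and record the number of adverse events". Section 2.1 describes the endpoint this way: "The total incidence of adverse events will be evaluated using CTCAE v4.03 from the time of informed consent to 21 days after study drug administration". Section 6.2 repeats the window, "from the time a patient signs consent to 21 days after study drug administration", and makes anyone who received even a partial dose evaluable.

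The infusion is "followed by tumor resection within 8-48 hours post-infusion" (section 4.1). Section 10.1 describes a single group. Nothing in section 10 divides adverse events by period, grade, attribution or patient.

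Section 7.3.2 has a five-level attribution scale that rates relation to study treatment. Its lowest level reads "Unrelated: AE is clearly NOT related to the study treatment". It has no option that names the resection or the disease. Section 4.3 refers every event of Grade 2 or higher that is at least possibly related to the external DSMB. The DSMB also reviews each patient's 21-day data before another patient is registered.

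**The concern.** With no comparator, the drug can be told apart from the operation only by when an event began and by clinical judgement of its cause. The planned count uses neither. It also includes events between consent and infusion, which the drug cannot have caused.

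The interval between infusion and incision is where acute effects would be least confounded, and there is reason to look there. Section 8.1.10 lists infusion reaction and low blood pressure as possible side effects. Section 1.2.1 reports a plasma half-life of about 2 to 9 minutes in monkeys, and section 1.2.3 a moderate fall in blood pressure at 8 mg/kg. A few such events could be hard to see in a total that also holds post-operative events. A high total could equally be misread as drug toxicity.

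**Working it through.** The plan states no figure to reproduce here. Section 10.2 sets n = 6, 7 or 8 on feasibility, with no event rate or precision target. What can be checked is how the window divides.

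Inputs:
- Post-dose follow-up: 21 × 24 = 504 h (sections 2.1 and 6.2).
- Dose to incision, *s*: 8 to 48 h (section 4.1). The infusion itself, about 20-50 minutes, is ignored.
- Consent to dose, *P* days: "Informed consent can be within 28 days prior to registration" (Table 5.1, footnote 1) and "Within 14 days of study registration, patients will receive intravenous NU-0129 one time" (section 4.6), so at most 28 + 14 = 42 days.

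**Post-dose time only.** The share after incision is (504 − *s*)/504.
- *s* = 48: 456/504 = 90.5%
- *s* = 8: 496/504 = 98.4%

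The dose-to-incision share is the remainder, 9.5% and 1.6%.

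**Window as defined, from consent.** The share after incision is (504 − *s*)/(504 + 24*P*), and the dose-to-incision share is *s*/(504 + 24*P*).

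| *P* (days) | Window (h) | After incision, *s* = 48 to 8 | Dose to incision, *s* = 8 to 48 |
|---|---|---|---|
| 0 | 504 | 90.5-98.4% | 1.6-9.5% |
| 7 | 672 | 67.9-73.8% | 1.2-7.1% |
| 14 | 840 | 54.3-59.0% | 1.0-5.7% |
| 21 | 1008 | 45.2-49.2% | 0.8-4.8% |
| 42 | 1512 | 30.2-32.8% | 0.5-3.2% |

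The post-incision share reaches one half when 24*P* = 504 − 2*s*. That is *P* = 17.0 days for *s* = 48 and 20.3 days for *s* = 8.

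**Hours at risk before incision.** For patients resected on schedule, the total lies between 6 × 8 = 48 and 8 × 48 = 384 patient-hours and can differ 48/8 = 6-fold between patients. These are not limits for the safety set. Section 4.9 keeps patients with no resection, or a resection after 48 h, evaluable for toxicity, and one unresected patient could contribute up to 504 h.

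**From time to events.** No rate is given, so this is an assumption only. With 1 to 5 post-surgical events and 0.1 to 1 pre-incision events per patient, the pre-incision share of the two together runs from 0.1/5.1 = 2% to 1/2 = 50%. The range is too wide to conclude which kind dominates.

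**What the pre-incision period can show.** Telemetry runs for at least 8 h after infusion, then vital signs at least every 4 h to 24 h. Table 5.1 schedules chemistry, coagulation and cholesterol only at screening and post-operatively, and the treatment-day CBC is pre-dose (footnote 5). Phosphorus and magnesium are marked for the treatment day without saying whether before or after the dose. Liver damage and hypercholesterolemia, also listed in section 8.1.10, would therefore first be looked for after surgery.

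**The case against.** The best defence is that much of the separation already exists outside section 10. Table 5.1 has distinct toxicity assessments at treatment and post-operatively, and section 8.1.11 has infusion start and stop times logged. Events are graded by CTCAE, and a surgical event can be coded as unlikely or unrelated. The DSMB sees related events quickly and every patient's data in turn. In a descriptive phase 0 study of 6-8 patients, a dated listing would show most of what a table would.

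This stands as a reason not to overstate the point. A reader might infer that the dose-to-incision period will never be reported, or that the trial cannot say whether NU-0129 was safe. The documents do not support either: events in that period are monitored, and nothing prevents a table by period. But attribution and DSMB review serve reporting and dosing decisions and do not enter the result that section 10.3.1 commits to. No listing is promised either.

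It might also be said that section 7.2.1 defines an adverse event by reference to a patient receiving study treatment, which could leave pre-dose events out. Sections 2.1, 4.3 and 6.2 nevertheless all open the window at consent.

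**Conclusion.** The concern holds as a reporting gap that should be closed. The primary result is an undivided count in which a short drug-only interval, 0.5-9.5% of the window, is pooled with pre-dose and post-operative time, without a comparator.

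Two stronger readings should be resisted. A reader might take 90-98% as the post-operative share of the primary window. It is the share of post-dose time only; from consent the share is about 30-98%. A reader might also infer that surgical events will swamp the count. A share of hours is not a share of events, and the documents give no rates.

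The figures assume resection within the planned 8-48 h and use the maximum consent-to-dose interval that the protocol allows.

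**What to change.** In section 10.3.1, state that the safety analysis covers all dosed patients, including those not resected or resected late. This also settles the tension between sections 4.9 and 6.2, which keep such patients, and the general paragraph in 10.3.3, which analyses patients who undergo surgery. Report adverse events by onset:

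1. consent to start of infusion;
2. start of infusion to incision, with hours at risk for each patient;
3. incision to Day 21.

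For a patient never resected, period 2 runs to Day 21. In each period give the number of patients with at least one event, the worst grade, and attribution on the section 7.3.2 scale, optionally with added options for surgery and disease. Record the clock time of onset from infusion to incision.

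Treat period 2 as the least confounded evidence on acute clinical and vital-sign effects only, given the laboratory schedule. Describe period 3 as drug plus surgery, with attribution as a judgement.

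The cost is a short protocol amendment with its approvals (section 11.2) and a small eCRF change for onset time and any added attribution options. No visits or patients are added. Counts per period will be small: no events in 6 to 8 patients still leaves a one-sided 95% upper bound on the per-patient event rate of 1 − 0.05^(1/6) = 39% to 1 − 0.05^(1/8) = 31%, so an empty period 2 must not be presented as proof of safety.

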4.3 Toxicity Management & Dose Delays/Modifications

Each patient will be assessed for the development of toxicity from the time of consent to 21 days post-dose. Toxicity will be assessed according to CTCAE v4.03. Any patient who receives at least one dose of study therapy will be evaluable for toxicity endpoints.

Patients should be closely observed for infusion-related reactions and any other form of toxicity. Treatment for infusion reactions, and all events, will be based on institutional guidelines. Grading and resolution of the event will be reported using CTCAE v4.03. For example, if a severe infusion reaction occurs, the infusion rate should be cut in half to 2.0-5.0mL/minute.

During the surgical resection, the resected tumor sample should be observed for potential discoloration. The locations and degree of discoloration must be carefully recorded and assessed for relationship to treatment with NU-0129.

There will be no dose delays or modifications as this is a single-dose therapy. However, each patient will be closely monitored for toxicities during the first 21 days after receiving study treatment. Any adverse event that is reported as a Grade 2 toxicity or higher, that is at least possibly related to NU-0129, will be referred to the external DSMB (Data Safety Monitoring Board) for review. The DSMB will review the event within 24 hours of notification to determine a plan for dosing future patients and immediate action if necessary. In addition, each patient's safety data will be reviewed at the end of the 21-day period post therapy and the DSMB will provide a recommendation for future dosing. No additional patients will be registered until the DSMB provides their analysis.

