10.2 Sample Size and Accrual

The sample size n=6, 7, or 8 was determined on the basis of feasibility of recruitment and of conducting the study. This is the first study in humans or this treatment, and it was felt that both the primary and secondary outcomes can be estimated with sufficient precision with such n, while few patients would be put to risk.

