10.3.3 Exploratory Objectives

To evaluate the Bcl2L12 expression levels and apoptotic markers in the tumor tissue post-treatment, and to evaluate preliminary response (Overall Survival and Progression Free Survival at 2 years, as well as Overall Response Rate) we will describe expression levels and PFS and OS Kaplan-Meier curves corresponding to in study time up to 24 months.

In general, all patients properly included in the study who undergo surgery for tumor removed will be included in the analysis. Thus, an incorrect treatment schedule or drug administration would result in exclusion from the analysis of the tumor accumulation study. All conclusions will be based on all eligible patients. Subanalyses may then be performed on the basis of a subset of patients, excluding those for whom major protocol deviations have been identified. However, these subanalyses may not serve as the basis for drawing conclusions concerning treatment efficacy, and the reasons for excluding patients from the analysis should be clearly reported.

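### The primary safety result is a total of adverse events, not tied to the dosed patients, so it does not show how many of the 6-8 patients were affected

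*Combined protocol and SAP*

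**What the plan says.** Section 10.3.1 gives the primary analysis in one sentence: to evaluate safety, "we will count and record the number of adverse events". No section plans the number or proportion of patients with an event, whether overall, by term, by grade or by relatedness.

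The endpoint is worded in two other places. Section 2.1 states: "The total incidence of adverse events will be evaluated using CTCAE v4.03 from the time of informed consent to 21 days after study drug administration". It does not define the unit of that incidence. Section 6.2 states: "Safety will be measured by recording adverse events using CTCAE v4.03".

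The plan does define who counts for safety. Section 6.2 says: "Any patient who has received at least a partial dose of NU-0129 will be evaluable for this endpoint". Section 4.3 says: "Any patient who receives at least one dose of study therapy will be evaluable for toxicity endpoints". Section 4.9 keeps a dosed patient evaluable for toxicity even if the resection is late or does not happen. Section 10.3.3, however, adds as a general rule that "all patients properly included in the study who undergo surgery for tumor removed will be included in the analysis", and the Statistical Methodology row of the Study Summary repeats it.

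On precision, Section 10.2 sets n at 6, 7 or 8 on feasibility and says that "both the primary and secondary outcomes can be estimated with sufficient precision with such n".

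**The concern.** Dosing, evaluability and sample size are all expressed per patient, but the planned primary result is expressed in events. The two can diverge widely. The definition in Section 7.2.1 takes in any unfavourable sign, symptom or laboratory finding, whatever its cause. Every patient is due a tumour resection 8-48 hours after the infusion. Tables 5.1 and 5.2 schedule toxicity assessments at dosing, after surgery and on Days 7, 14 and 21. Several events from one patient are therefore likely. That is an inference from the design; the documents give no event rate.

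The same total can come from one badly affected patient or from a single event in every patient, and for a first-in-human agent these carry very different messages. If the unit stays undefined, it will be chosen after the data are seen. The precision statement in Section 10.2 also has nothing to attach to, because Section 10.3.1 names no proportion, rate or interval.

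**Working it through.** There is no figure in the plan to reproduce: n rests on feasibility, and no event rate, interval width, alpha or power is stated. The check is how much a given event total says about the number of patients affected.

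**Inputs.** n = 6, 7 or 8 (Section 10.2). Evaluable for safety: every patient with at least a partial dose (Section 6.2). The event totals below are assumptions for illustration.

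**Step 1: what a total allows.** With T events in n patients, the number with at least one event can be anything from 1 to min(n, T).

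| Assumed total T | n | Fewest affected | Most affected |
|---|---|---|---|
| 8 | 8 | 1/8 = 12.5% | 8/8 = 100% |
| 6 | 8 | 1/8 = 12.5% | 6/8 = 75% |
| 12 | 6 | 1/6 = 16.7% | 6/6 = 100% |

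**Step 2: the two extremes for T = 8, n = 8**, with exact (Clopper-Pearson) 95% intervals.

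- All events in one patient, x = 1. The lower limit is 1 - 0.975^(1/8) = 0.003. The upper limit is the p that solves (1-p)^8 + 8p(1-p)^7 = 0.025, which is 0.527. Result: 12.5% (0.3%-52.7%).
- One event in each patient, x = 8. The lower limit is 0.025^(1/8) = 0.631. Result: 100% (63.1%-100%).

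These two intervals do not overlap, yet Section 10.3.1 would report 8 in both cases. Dividing by n does not help: 8/8 = 1.0 event per patient either way.

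**Step 3: what a patient-level result would look like.** Exact 95% intervals for x affected of n dosed:

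| Affected | n = 6 | n = 8 |
|---|---|---|
| 0 | 0%-45.9% | 0%-36.9% |
| 1 | 0.4%-64.1% | 0.3%-52.7% |
| 2 | 4.3%-77.7% | 3.2%-65.1% |

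With none affected, the upper limit is 1 - 0.025^(1/n); for n = 7 it is 41.0%.

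**Step 4: which patients form the denominator.** Sections 6.2, 4.3 and 4.9 point to dosed patients. The general rule in Section 10.3.3 points to patients who had surgery. A patient who was dosed but not resected is inside the first set and outside the second. Section 10.3.1 cites neither.

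**The case against.** Several points on the other side have force.

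- **Recording rules limit splitting.** Section 7.2.1 asks for the diagnosis rather than its component signs when a diagnosis has been made, and excludes pre-existing conditions that do not worsen. Section 7.1 follows each event to resolution, which does not suggest a fresh record at each visit. This stands in part. It reduces double counting of one episode, but it gives no rule for recurrences and does not stop one patient from having several distinct events.
- **The DSMB sees patients, not totals.** Under Section 4.3, related events of Grade 2 or higher are referred to the DSMB, each patient's data are reviewed at the end of the 21 days, and registration waits for its analysis. Decisions during the trial are therefore unlikely to confuse one badly affected patient with several mildly affected ones. This stands, but it is monitoring. It does not alter what Section 10.3.1 will report.
- **A Phase 0 study of this size is descriptive.** True, and x of n patients is also a descriptive result. Adding an exact interval is partly a matter of preference.
- **Any-cause events after a craniotomy may approach n of n**, so the headline proportion could say little. This is fair, though the documents give no rate. It is why the split by grade and relatedness matters most.

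A reader might infer that the plan has no safety denominator at all. It has one, in Sections 6.2 and 4.3, and total incidence could even be read as patients or as events per patient. The gap is that the unit is undefined and the count is not linked to that set.

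A reader might also infer that any interval on the event total would be too narrow. The plan proposes no such interval. Whether one would fall short depends on the number of events per patient and how strongly they cluster, which the documents do not give. With few events and weak clustering there may be no shortfall.

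**Conclusion.** The concern holds as a defect in the stated primary measure: an event total cannot recover the number of patients affected. The size depends on the data. In the illustration the same reported figure covers affected proportions from 12.5% to 100%. This assumes only that one patient can have more than one event, which the definition in Section 7.2.1 allows; the total of 8 is illustrative.

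It is a reporting correction that should be made, at the lower end of that category. The underlying records are kept by patient, the DSMB review is by patient, and the right table can still be produced. It does not bear on n or on the conduct of the trial.

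**What to change.** Reword Section 10.3.1, and align Section 2.1 with it, along these lines:

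- The primary result is the number and proportion of all dosed patients (the Section 6.2 population, partial doses included) with at least one adverse event from consent to 21 days after dosing.
- Count each patient once per CTCAE term, at the worst grade. Present the result overall, by maximum grade, and by at least possible relation to NU-0129, and treat the grade and relatedness splits as the informative part.
- Give exact binomial 95% intervals on the number dosed.
- Keep the total number of events as a supporting column, with a listing of events by patient.
- State in Section 10.3.3 and in the Study Summary that the surgery-only rule does not apply to safety, and use the Section 6.2 wording in Section 4.3, so that a partial dose clearly counts.

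The cost is a few sentences and one summary table. No new data and no change in n are needed. The downside is that the intervals will look wide: even 0 of 8 affected leaves an upper limit of 36.9%. That is an accurate statement of what 6-8 patients can show, and the precision claim in Section 10.2 should be read against it.
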